Our ultimate goal is to determine whether an individually prescribed homeopathic medicine has an effect greater than a placebo and is a viable treatment option to improve fatigue and quality of life for patients suffering from the symptoms of Post-acute COVID-19 Syndrome. We hope to achieve this goal by conducting a clinical trial that is scientifically rigorous and clinically relevant. Because such a trial would be costly, we first need to do a pilot study that demonstrates our ability to conduct a fullscale trial successfully. Expected results of this pilot study will be to obtain sufficient experience and preliminary feasibility data to justify a larger clinical trial of this hypothesis.

Technical Objectives

Our objectives for the study are to: 1) identify efficient means of recruiting subjects, 2) test and refine our initial study design and treatment protocol, 3) evaluate the instruments for assessing treatment outcomes, 4) estimate sample sizes that will be required in the full-scale trial, 5) determine which homeopathic medicines are most often prescribed for this syndrome, and 6) determine whether there is a measurable effect size difference or positive trend in reduction of symptoms in patients treated with homeopathy.

Methods

Overview: In this double-blind pilot study, 66 patients who have tested positive for COVID-19 and

who have had unexplained fatigue for at least 60 days, as well as at least one other symptom of Postacute COVID-19 syndrome will be randomized to one of two treatment arms: classical homeopathy or placebo. Treatment will be provided by trained homeopathic practitioners, who will see the patients at 4 week intervals over the course of 12 weeks. Fatigue scores and general health status as measured by the SF-36 will be measured at entry to the study and at 4 week intervals for 12 weeks. The MYMOP score of specific symptoms will be administered at entry to the study and at the end of 12 weeks.

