Randomization and blinding: Subjects in the study will be randomly assigned to receive individualized homeopathic treatment or placebo (1 : 1). After the confirmation of eligibility, subjects will be randomized with concealment. Every subject will be assigned with a number and a third party will randomize the subjects to each of the 2 study groups using computer generated random numbers. Randomization will be stratified by age (< or > 50) and duration of Long Covid symptoms (< or > 6months), in permuted blocks of four or six. Randomization will be known only to the homeopathic pharmacist, who will not break the code until after treatment of each subject is completed. An exception to this will be when a research subject suffers an unexplained severe event. In such a case, the randomization code will be broken and the subject withdrawn from the study.

Follow-up: Subjects will have follow-up visits by video with the homeopathic practitioners at 4, 8, and 12 weeks following the initial consultation. At each of these visits, the patients will be reevaluated, adverse side effects will be inquired about, and the classical homeopathic prescription will be renewed or revised, which will again be filled by the homeopathic pharmacist and mailed to the subjects. Although the specific homeopathic prescription might change, subjects randomized to each group will continue to receive placebo or active medicines throughout the study.

The subjects will also complete online questionnaires at 4, 8 and 12 weeks after the initial visit to

evaluate outcomes. At the end of the 12 week study period, those subjects who received placebo will be given the option to receive a verum homeopathic medicine and an additional follow-up visit after 6 weeks will be scheduled for them.

Outcomes:

The primary outcome measurements:

- Fatigue Assessment Score (FAS) at baseline, week 4, week 8 and week 12
- General health status, using the SF-36 at baseline, week 4, week 8 and week 12 Secondary outcome measurements:
- Measure Yourself Medical Outcomes Profile (MYMOP), in which each patient chooses the two most bothersome symptoms to record and follow (at study entry and at the end of 12 weeks)
- The number of subjects who have FAS ≤ 21 will be compared at week 4

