Analysis: Because this is a pilot study with a small sample size, statistical tests are unlikely to reveal any statistically significant differences. However, the data will be summarized and analyzed as if this were a full-scale trial in an intention to treat analysis by the study statistician.

- Demographic data and baseline features will be compared using independent sample t-test and chi-square test for continuous and categorical variables respectively. (Age, sex, duration of symptoms, co-morbidities)
- Missing values will be handled by single imputation by last observation carried forward to handle missing data at the analytical stage.
- The Fatigue assessment scale (FAS) and the SF-36 (8 domains) from baseline (Day=0) and at 4-, 8-, and 12-week follow up will be analyzed by repeated-measure analysis of variance (treatment x time interaction).
- The Measure Yourself Medical Outcomes Profile (MYMOP) collected at baseline and at week 12 will be analyzed by independent sample t-test if normal or Wilcoxon ran sum test if not.
- The proportion of subjects who 'return to normal' (ie have FAS ≤21) will be compared at week 4 with chi-square test.
- Analyses will be performed using SPSS software, version 26. Two-tailed P < 0.05 will be used to denote statistical significance.
- Evidence of non-significant trends will be noted, and the variability of the FAS will be used for sample size estimation for the full-scale trial.

All modifications to this study will be approved by the Human Subjects Committee. Any adverse

event that occurs temporally related to participation in the study will be documented, whether or not it is considered to be related to the homeopathic medicines. Serious and unexpected adverse experiences will be immediately reported by telephone to the Human Subjects Committee.

References

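### Age group and symptom duration stratify the randomisation but enter no outcome analysis, and baseline features are compared by significance tests; power may be lost to the extent that the strata predict outcome

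*Combined protocol and SAP*

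**What the plan says.** Under Methods, Randomization and blinding: "Randomization will be stratified by age (< or > 50) and duration of Long Covid symptoms (< or > 6months"). Two factors with two levels each make four strata, and allocation within each stratum is "in permuted blocks of four or six".

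Under Methods, Analysis: "Demographic data and baseline features will be compared using independent sample t-test and chi-square test". The features listed are "Age, sex, duration of symptoms, co-morbidities", so two of the four are the stratification variables.

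The same paragraph then gives every outcome analysis. FAS and the SF-36 domains "will be analyzed by repeated-measure analysis of variance (treatment x time interaction"). MYMOP gets a t-test, or a rank-sum test if the data are not normal. The proportion with FAS of 21 or below at week 4 gets a chi-square test. The criterion throughout is "Two-tailed P < 0.05 will be used to denote statistical significance". No analysis names age, symptom duration or any other covariate, and nothing is said about how the baseline test results will be used. The variability of FAS is to feed the sample size of the full-scale trial.

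**The concern.** Stratified blocks make the arms more alike on age group and symptom duration. If those factors are prognostic, the treatment difference varies less from trial to trial than an unstratified analysis assumes. An analysis that omits them leaves their variance in the error term, so its standard error is too large. The estimate is not biased and false positives are not inflated. What can be lost is precision.

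The baseline tests add nothing in place of this. Any difference after concealed randomisation is due to chance, and for age and duration the design itself restrains the difference.

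The stake is modest but falls on the pilot's own purpose. Estimating the sample size of the full trial is a stated objective, and a pilot that never models its strata cannot show whether they are worth keeping.

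**Working it through.** **Inputs from the document.** N = 66 ("In this double-blind pilot study, 66 patients who have tested positive for COVID-19"), allocated 1:1, so n = 33 per arm; four strata; blocks of four or six; two-sided alpha 0.05.

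**The plan's own figure.** The 66 comes with no effect size, SD, power or dropout, so it cannot be reproduced as a power calculation. It does fit the recruitment target: 15 to 20 a month for 4 months gives 60 to 80. For scale, 80% power needs (1.960 + 0.842) × √(2/33) = 0.69 SD.

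**Assumptions.** R², the share of variance in the compared quantity that the strata explain, is not stated; 0 to 20% is used. The effect is taken as 0.5 SD.

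**Single-time-point comparison.** Let s = √(2/33) = 0.246 and k = √(1 − R²). With the arms balanced on the strata, the true standard error is about s·k, while the unadjusted test uses s.

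- Type I error, unadjusted: 2[1 − Φ(1.96/k)]
- Power, unadjusted: Φ((0.5 − 1.96s)/(s·k))
- Power, adjusted: Φ(0.5/(s·k) − 1.96)

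| R² (assumed) | k | Type I error, unadjusted | Power, unadjusted | Power, adjusted |
|---|---|---|---|---|
| 0 | 1.000 | 5.0% | 52.8% | 52.8% |
| 5% | 0.975 | 4.4% | 52.9% | 54.9% |
| 10% | 0.949 | 3.9% | 53.0% | 57.2% |
| 20% | 0.894 | 2.8% | 53.2% | 62.2% |

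Simulated trials with the actual blocking (6,000 per setting; 35% in one age stratum and 50% in one duration stratum assumed) gave unadjusted type I errors of 5.2%, 3.9% and 2.9% at R² of 0, 10% and 20%, against 5.2%, 4.7% and 4.8% adjusted. Separate simulations at 0.5 SD put the gain from adjustment at about 4 to 5 points of power at R² of 10% and about 9 to 10 at 20%. At R² = 0, power with and without adjustment agreed within 0.5 points.

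These figures describe a t-test, so they apply most directly to MYMOP. The direction is the same for the week-4 chi-square test; its size was not computed.

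**Treatment-by-time test (FAS, SF-36).** Each patient's own level drops out of this test. In 4,000 simulated trials per setting:

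| Stratum effect | Type I error | Power |
|---|---|---|
| None | 5.0% | 71% |
| On level only | 4.9 to 5.0% | 70 to 72% |
| On change over time | 4.0 to 4.3% | 68 to 70% |

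A further simulation put the power lost by omitting the strata at about 2 points when R² is 10% and 4 points when it is 20%, with the strata predicting change.

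**What has to be added to that model.** In a simulated dataset of 66 patients and four visits, adding the two factors as between-subject main effects left the treatment-by-time F exactly unchanged (0.1971 on 3 and 192 df). Only factor-by-time terms alter it. They use 2 factors × 3 time contrasts = 6 df: the error df go from 3 × (66 − 2) = 192 to 3 × (66 − 4) = 186.

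**Planning variance.** If the full trial adjusts for strata, an unadjusted variance overstates its N by the factor 1/(1 − R²): 1.05, 1.11 and 1.25 at R² of 5%, 10% and 20%.

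**Baseline tests.** In simulations of this design with assumed age and duration distributions, the age test reached P < 0.05 in about 0.2% of trials and the duration test in about 0.2 to 0.5%. Both are nearly empty by construction.

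**The case against.** The strongest reply is that this is a pilot whose plan already expects no significant differences, that any error is on the conservative side, and that the primary test is largely immune. Much of that stands. No false positive claim and no bias can follow, and strata that shift only the level of FAS or SF-36 cost the treatment-by-time test nothing. It does not dispose of the point: the plan still commits to a full-trial style of analysis at the 5% level, and FAS variability is a planned output.

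Three stronger readings are tempting, and the documents do not support them.

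- *Power is certainly lost, by up to 10 points, on the primary outcomes.* The 10-point figure belongs to a single-time-point t-test at an assumed R² of 20%. It is not evidence about the treatment-by-time test, and the documents give no R².
- *Four baseline tests at 5% carry a 19% chance of a spurious imbalance.* That calculation (1 − 0.95⁴ = 18.5%) treats the tests as independent and unstratified. The blocks restrain age and duration, and simulation of this design gives about 10 to 12%. Nor does the plan tie any adjustment or decision to these P values, so later misuse is only a possibility.
- *The strata are unusable as covariates because exactly 50 years or exactly 6 months belongs to neither side.* Both values are reachable under Eligibility (ages 18 to 64; at least 60 days of fatigue). But a third party must place every subject in some stratum, and that stratum can serve as the covariate. This is a wording clarification only.

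**Conclusion.** The point holds in a limited form. The two stratification factors are absent from every outcome analysis, and the baseline P values have no inferential use. The resulting tests are conservative to a degree that depends on an unstated quantity. For the unadjusted between-arm comparisons, the cost runs from nothing at R² = 0 to about 10 points of power at 0.5 SD at R² = 20%, with type I error near 3%; these are t-test figures. For FAS and SF-36 it is roughly 0 to 4 points, and only if age or duration predicts change. The planning variance may overstate the N of a strata-adjusted full trial by 0 to 25% over the same assumed range. None of this threatens the validity of the pilot. The change is worth making because it costs almost nothing.

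**What to change.** - Include age group and duration group, coded as used in the randomisation, in every between-arm model.
- FAS and SF-36: add age-group-by-time and duration-group-by-time terms (6 df). Main effects alone do not change the treatment-by-time test.
- MYMOP: fit a linear model with both factors as covariates.
- FAS of 21 or below at week 4: use a Cochran-Mantel-Haenszel test over the strata, or logistic regression with both factors. Name one in advance.
- Base the full-trial sample size on the strata-adjusted FAS variance.
- Present baseline features by arm descriptively, without P values.
- State which stratum contains age exactly 50 and duration exactly 6 months.

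Cost: plan wording and a few model terms. No new data and no extra patients are needed, and the loss if the strata prove unrelated to outcome is negligible.

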Recruitment: Subjects will be recruited from advertisements on Facebook. We hope to enroll 15-20 patients per month during the 4 month enrollment period. We will use an online survey to screen potential subjects to determine eligibility. Those who are eligible will be scheduled for a telephone screening appointment, during which eligibility will be confirmed and informed consent will be obtained using a consent form approved by the Southwest College of Naturopathic Medicine Human Subjects Committee. Baseline questionnaire data will be collected, including the Fatigue Assessment scale (FAS), the SF-36 quality of life survey, and the Measure Yourself Medical Outcomes Profile (MYMOP).

Eligibility: Patients entered into the study will be ages 18-64 and have a confirmed diagnosis of COVID-19 by previous PCR testing. They will also have a history of persistent, unexplained fatigue for at least 60 days since diagnosis of COVID-19, one other symptom consistent with the syndrome, and a FAS score of 22 or above. Subjects must also have adequate cognitive function to be able to give informed consent and be technologically competent to complete online forms and perform video calls. They must also be willing to fill out regular questionnaires and to use homeopathic medications.

Exclusions: Patients taking steroids, immunosuppressives, or opioid analgesics or who have opioid or other substance dependence and/or are undergoing treatment for substance abuse will be excluded from the study. Patients who were treated in an Intensive Care Unit for Covid-19 and those with concurrent health problems such as active cancers, clinically significant kidney, heart, or hepatic impairment will be excluded. Those diagnosed prior to COVID-19 infection with chronic fatigue syndrome, fibromyalgia, Lyme disease, or chronic psychiatric or neurological illness will also be excluded. Also excluded will be women with suspected or confirmed pregnancy and those who are breastfeeding, those who are enrolled in another trial. Those who are currently being treated by a homeopathic practitioner will also be excluded as well as those who have started a new medication or treatment for Post-acute Covid-19 within the past two months.

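### Last observation carried forward is the only missing-data rule and has no sensitivity analysis; it can modestly bias the pilot's effect estimates when dropout differs by arm or an effect builds over time

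*Combined protocol and SAP*

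**What the plan says.** The Analysis section handles missing data in one sentence: "Missing values will be handled by single imputation by last observation carried forward to handle missing data at the analytical stage". It is not limited to any outcome. The documents state no reason for missingness, no expected dropout rate, no alternative method and no sensitivity analysis.

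The rule feeds these analyses:

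- **FAS and the eight SF-36 domains**, at baseline and weeks 4, 8 and 12, by repeated-measures ANOVA (treatment x time).
- **Return to normal fatigue at week 4**: "ie have FAS ≤21) will be compared at week 4 with chi-square test". Under Eligibility, entry requires "one other symptom consistent with the syndrome, and a FAS score of 22 or above".
- **MYMOP**, measured twice only: "The Measure Yourself Medical Outcomes Profile (MYMOP) collected at baseline and at week 12".

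The sixth item under Technical Objectives is to "determine whether there is a measurable effect size difference or positive trend in reduction of symptoms in patients treated with homeopathy". The Analysis section adds that "the data will be summarized and analyzed as if this were a full-scale trial in an intention to treat analysis" and that "Evidence of non-significant trends will be noted". Some missing data are foreseen: after an unexplained severe event, "the randomization code will be broken and the subject withdrawn from the study" (Randomization and blinding). No outcome collection after withdrawal is described.

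**The concern.** LOCF assumes that a subject who leaves would have stayed at the last observed score. In a condition where both arms may improve over 12 weeks, leavers are then credited with only part of the improvement. If one arm loses more subjects, loses them earlier, or loses a different kind of subject, the arms are held back by different amounts and a difference appears that treatment did not cause. With no true effect, the mean difference is unbiased only when dropout has the same rate, timing and relation to outcome in both arms. If treatment does work and its effect grows with time, leavers contribute only part of it, so the estimate shrinks even when dropout is balanced.

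Two further consequences depend on a reading of the rule. If baseline counts as an observation that can be carried, as the intention-to-treat wording suggests, a subject missing week 4 is always counted as not normal, because the entry score was at least 22. A subject missing the week-12 MYMOP is given the baseline score, that is, no change.

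At stake is the sixth objective. An effect size or a positive trend is read from point estimates, which LOCF can move in either direction, and no planned analysis would show that it had.

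**Working it through.** **Inputs from the documents.** 66 subjects randomised 1:1, so 33 per arm; the visit schedule; FAS of 22 or above at entry; FAS of 21 or below as the week-4 outcome. The plan has no figure of its own to reproduce.

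**Assumed inputs.** FAS SD 7 at each visit; correlation 0.6 (equal between visits, or AR(1)); 6 points of improvement common to both arms by week 12; leavers split equally among last visit at baseline, week 4 and week 8; missingness random within arm unless stated.

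**Share of improvement lost per leaver.**
- Linear course: leavers have completed on average (0 + 1/3 + 2/3)/3 = 1/3, so 2/3 is lost.
- All change by week 4: (0 + 1 + 1)/3 = 2/3 completed, so 1/3 is lost.

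An arm's LOCF mean improvement is therefore: true improvement x (1 - dropout x share lost).

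**1. No true effect, unequal rates.** Spurious week-12 difference = gap in dropout x 6 x share lost.

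| Dropout | Linear | All by week 4 |
|---|---|---|
| 5% vs 10% | 0.05 x 6 x 2/3 = 0.2 | 0.05 x 6 x 1/3 = 0.1 |
| 10% vs 20% | 0.10 x 6 x 2/3 = 0.4 | 0.10 x 6 x 1/3 = 0.2 |
| 10% vs 30% | 0.20 x 6 x 2/3 = 0.8 | 0.20 x 6 x 1/3 = 0.4 |

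The arm that loses fewer subjects looks better.

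**2. No true effect, equal 20% dropout.**
- Different timing: if one arm loses subjects only after week 8 and the other only before week 4, the difference is 0.2 x 6 x (1 - 1/3) = 0.8.
- Different relation to outcome (simulated, linear course, equal correlation): random loss in one arm and loss of the 20% with the worst week-12 change in the other gives mean changes of -5.2 and -6.4. The true value is -6 in both arms.

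**3. True 4-point effect** (10 points active, 6 placebo).

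| Dropout active/placebo | Linear | All by week 4 |
|---|---|---|
| 20%/20% | 10(1 - 0.133) - 6(1 - 0.133) = 3.5 | 10(1 - 0.067) - 6(1 - 0.067) = 3.7 |
| 10%/30% | 10(1 - 0.067) - 6(1 - 0.2) = 4.5 | 10(1 - 0.033) - 6(1 - 0.1) = 4.3 |
| 30%/10% | 10(1 - 0.2) - 6(1 - 0.067) = 2.4 | 10(1 - 0.1) - 6(1 - 0.033) = 3.2 |

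Simulation agrees with these figures. A separate simulation with SD 8 gave 3.48, 4.55 and 2.41 for the linear column.

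**4. Against sampling error.** Standard error = SD of change x sqrt(2/33) = SD of change x 0.246.
- Equal correlation: SD of change = 7 x sqrt(2 x 0.4) = 6.26, standard error 1.54.
- AR(1), 0.6 cubed = 0.216: SD of change = 7 x sqrt(2 x 0.784) = 8.77, standard error 2.16.
- SD of change 9.3 to 10: standard error 2.3 to 2.5.

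**5. P-values and variability.** With no effect and 10% vs 30% dropout, the simulated type I error of the repeated-measures test is 5.2-6.8% with Greenhouse-Geisser correction, and 5.8-7.3% uncorrected with equal correlation. A t-test on week-12 change with SD 8 gave 7.5%. With SD 8, the SD of change under LOCF was 6.87 to 7.36, against about 7.1 with complete data.

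**6. Week-4 proportion, if baseline is carried.** Observed rate = true rate x (1 - share missing). With a true 30% in both arms and 10% vs 30% missing: 27% vs 21%, and 0.06 x 33 = about 2 patients. With 3% vs 10% missing: 29.1% vs 27%, or 0.7 of a patient.

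**7. MYMOP, if baseline is carried.** 20% dropout in both arms multiplies a true difference by 0.80. With no effect, 10% vs 30% dropout creates a difference of 20% of the common mean change; 5% vs 10% creates 5% of it.

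**8. The alternative has its own weakness.** With dropout random within arm, a mixed model on observed visits returns 4.0 in all six cells of step 3. If leavers truly stop improving (linear course), the truth for all randomised subjects is 3.5, 4.5 and 2.4. LOCF is then right, and the mixed model, still at 4.0, is off by +0.5, -0.5 and +1.6.

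**The case against.** The strongest reply is that the design works against unequal dropout. The trial is double-blind with an indistinguishable placebo, and placebo subjects are offered active treatment only after week 12, which is a reason to stay. If treatment does nothing, dropout should be alike in expectation. With a common 20% rate, a gap of 7 or more leavers between arms of 33 arises by chance in about 4.5% of trials (binomial). This stands: 10% vs 30% is an unfavourable case, not the expected one. It does not cover dilution of a building effect, which needs no imbalance.

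It is also fair that this is a pilot. The plan itself expects few significant results, and the one quantity it names for sizing the full-scale trial, FAS variability, is barely touched. A reader might infer that LOCF invalidates the tests or the later sample size; steps 4 and 5 do not support that. A reader might also infer that the rule favours homeopathy. The documents do not support that either: the direction depends on which arm loses more, and the withdrawal rule shows only that some data may be missing, not that the arms will differ.

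Counting week-4 leavers as not normal and MYMOP leavers as unchanged are likely readings, not stated text. The plan does not say that baseline may be carried, or that MYMOP is analysed as change.

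Finally, preferring a mixed model could be called taste, since LOCF is right in step 8 if leavers stop improving. That is why neither method should stand alone.

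**Conclusion.** The concern holds in a limited form. A single untested assumption governs every missing outcome, and it can bias the estimates that the sixth objective and the noted trends rely on. Under the assumed inputs, the spurious FAS difference is 0.1-0.2 points for a small dropout imbalance and 0.4-0.8 for a large one. A true 4 points that builds linearly can read as anything from 2.4 to 4.5. Against a standard error of about 1.5-2.5 this is modest, and the sizes would change with other dropout rates, courses or SDs, none of which the documents supply.

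The documents do not support the stronger statement that LOCF is biased in every case. With no effect, and with dropout alike in rate, timing and relation to outcome, the mean difference is unbiased. Severity lies between minor and should-fix: it is a cheap improvement, not a flaw that undermines the pilot.

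**What to change.** - Analyse FAS and SF-36 with a likelihood-based mixed model for repeated measures on all observed visits (treatment, visit, treatment x visit, baseline). Keep LOCF as a sensitivity analysis.
- Report dropout by arm and visit.
- Add one missing-not-at-random sensitivity analysis, for example delta-adjusted, running from zero to the case where leavers keep no further improvement. With a linear course and a shortfall of 2/3 of each arm's improvement, the mixed-model 4.0 moves to 3.5, 4.5 and 2.4 in the three dropout patterns, so this range covers the case where LOCF is right.
- State whether baseline may be carried forward. For FAS of 21 or below at week 4, and for MYMOP, show a result that does not carry baseline (for example multiply imputed FAS scores, and week-12 MYMOP adjusted for baseline) beside the one that does.

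**Cost.** Part of the Analysis section must be rewritten, with some extra analysis work. Intervals may be slightly wider, and the methods must be checked against SPSS version 26. Visits, sample size and treatment do not change.

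### For the FAS score and the SF-36 domains the plan names only a non-directional treatment-by-time test: no primary contrast and no baseline-adjusted difference with a confidence interval

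*Combined protocol and SAP*

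**What the plan says.** All references are to the combined protocol and SAP.

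- **Analysis.** FAS and SF-36 scores "from baseline (Day=0) and at 4-, 8-, and 12-week follow up will be analyzed by repeated-measure analysis of variance (treatment x time interaction"). Treatment by time is the only effect named. Baseline enters as one of the four response levels, not as a covariate. No sphericity correction is mentioned.
- **Outcomes.** The first primary outcome is listed as "Fatigue Assessment Score (FAS) at baseline, week 4, week 8 and week 12", and the SF-36 is listed for the same visits. No visit is ranked above another. A secondary outcome compares the proportion with FAS ≤21 at week 4, tested by chi-square.
- **Technical Objectives.** Objective 6 is to "determine whether there is a measurable effect size difference or positive trend in reduction of symptoms"; objective 4 is to estimate sample sizes for the full-scale trial.
- **Analysis, on pilot status.** Significance is not expected, but "the data will be summarized and analyzed as if this were a full-scale trial", and "Evidence of non-significant trends will be noted".
- **Randomization and blinding.** "Randomization will be stratified by age (< or > 50) and duration of Long Covid symptoms (< or > 6months"). Neither factor appears in the planned analysis.

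No section specifies a between-arm difference in FAS or SF-36 scores, an effect-size estimator or a confidence interval.

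**The concern.** A test on 3 degrees of freedom asks whether the arms' profiles differ in any way across four visits. A significant result does not say which arm did better, when, or by how much. A non-significant result, which the plan expects, says little more. For a pilot with an effect-size objective, the informative output is the estimate and its interval, and that is what the plan leaves out.

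For the primary FAS score, the visit on which a trend will be judged is also open. It could be chosen after the arm means are seen. The test is often less efficient as well, because it spreads its sensitivity over three contrasts and does not use baseline as a covariate.

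**Working it through.** **Degrees of freedom.** Two arms, four visits, 66 subjects: interaction df = (2−1)(4−1) = 3; univariate error df = (66−2)×3 = 192. The protocol gives no derivation for 66, so there is no stated power to reproduce.

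**Inputs.** From the documents: 66 subjects, 1:1, so 33 per arm; two-sided 0.05. Assumed, because the documents are silent: SD 7 and effect 4 points (4/7 = 0.57 SD). The within-subject correlation is either compound symmetry (CS) 0.5, 0.6 or 0.7, or decaying, AR(1) 0.7 or 0.8.

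**One case by hand (CS 0.6).**

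- Interaction noncentrality: λ = (33/2) × Σ(δ_t − mean δ)² / [49 × (1 − 0.6)].
- Linear build-up (δ = 0, 1.33, 2.67, 4; mean 2): the sum is 8.89, so λ = 16.5 × 8.89 / 19.6 = 7.48. Noncentral F(3,192) gives power 0.61.
- Complete by week 4 (δ = 0, 4, 4, 4; mean 3): the sum is 12, so λ = 16.5 × 12 / 19.6 = 10.1, power 0.76.
- Baseline-adjusted week-12 difference: SE = 7 × √(1 − 0.36) × √(2/33) = 1.38; (4/1.38)² = 8.4 on a single degree of freedom. Power is about 0.81 for both shapes.

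**All scenarios.** 4,000 simulated trials each, complete data. The interaction is Greenhouse-Geisser corrected; the contrast comes from the mixed model described in the fix, with unstructured covariance.

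| Correlation | Build-up: interaction | Build-up: week 12 | By week 4: interaction | By week 4: week 12 |
|---|---|---|---|---|
| CS 0.5 | 0.50 | 0.75 | 0.65 | 0.75 |
| CS 0.6 | 0.60 | 0.81 | 0.74 | 0.80 |
| CS 0.7 | 0.73 | 0.88 | 0.88 | 0.89 |
| AR(1) 0.7 | 0.48 | 0.68 | 0.64 | 0.69 |
| AR(1) 0.8 | 0.61 | 0.75 | 0.79 | 0.75 |

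Repeating this with simple ANCOVA as the contrast agrees within about 2 points (build-up: interaction 0.47–0.74, week 12 0.67–0.89).

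- *Average of weeks 4–12, same model:* 0.57–0.77 for build-up and 0.91–0.98 for an effect complete by week 4. It is above the corrected interaction in all ten cells, but 9–11 points below week 12 for build-up.
- *Effect at week 4 only (0.6 SD):* interaction 68–92%, average 20–30%, week-12 contrast 5–6%, which is its null rate.
- *Type I error:* uncorrected interaction 5.2–5.6% under CS and 6.3–6.7% under AR(1); corrected 4.8–5.2%; mixed model 4.6–5.5%. The unnamed sphericity correction matters, but only slightly.

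**Precision.** The 95% half-width at week 12 from raw arm means is 2.0 × 7 × √(2/33) = 3.4 points. Baseline adjustment multiplies this by √(1 − ρ²), where ρ is the baseline-to-week-12 correlation: 2.5 at ρ = 0.7 and 3.2 at ρ = 0.7³ = 0.343. The fitted mixed model gave 2.5–3.3.

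**The case against.** **It is a feasibility pilot that claims no power.** This stands as a limit on severity. At an effect of 0.3 SD under AR(1) 0.7 both tests are weak: 0.16 against 0.23 for build-up, 0.21 against 0.25 for an early effect. It does not answer the missing estimate and interval, which matter more when significance is not expected.

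**The data will be summarized and trends noted.** Arm means by visit would show direction and timing, so the plan is not silent on them. They would be unadjusted, with no planned interval and no visit fixed in advance.

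**Week 12 is not uniformly better.** This stands.

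- The plan does not restrict the ANOVA to its univariate form. With an effect complete by week 4 and AR(1) 0.8, the multivariate interaction has power 0.87 against 0.76 for week 12. For build-up under the same correlation the order reverses, 0.45 against 0.76.
- Eligibility requires FAS of at least 22, which truncates baseline; the table ignores this. If the cut is assumed to fall at the underlying mean, an effect complete by week 4 gives 0.80 (corrected interaction) against 0.83 (week 12) for CS 0.6, and 0.71 against 0.67 for AR(1) 0.7. In these two structures the build-up advantage remains, at about 14–16 points.

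**Readings that the documents do not support.** A reader might infer that FAS is tested only by the interaction; the week-4 comparison of FAS ≤21 is a second, planned between-arm test at a named visit. A reader might also infer that including baseline as a response level, or omitting the randomization factors, makes the test invalid. Including baseline does not bias it. In the simulations, omitting the strata from the week-12 model was conservative: null rejection at CS 0.6 was 4.1% and 2.9% when each factor shifted the 12-week change by 2 and 5 points.

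**Conclusion.** The point holds as a gap in estimation and pre-specification. For the FAS score and the SF-36 domains the plan yields a non-directional test and no treatment difference with an interval, while objective 6 asks for an effect size or trend. That conclusion needs no assumed input.

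The efficiency argument is conditional on an assumed SD, effect, correlation and effect shape. For an effect that builds to week 12, the adjusted contrast gains 14 to 25 points of power over the Greenhouse-Geisser-corrected interaction. For an effect complete by week 4 it ranges from about 10 points better to 4–5 worse, and about 11 worse than the multivariate test under AR(1) 0.8. Baseline truncation reduces the advantage further. It would be wrong to conclude that the planned test is biased, that the contrast always wins, or that the trial is invalid. This is a cheap reporting and efficiency improvement.

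**What to change.** Before any outcome is seen by arm, amend the Analysis section as follows.

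1. Name the week-12 FAS difference between arms as the primary contrast. The reason is what it estimates: week 12 ends the placebo-controlled period, after which placebo subjects are offered active treatment.
2. Estimate it with a 95% CI from a mixed model on the scores at weeks 4, 8 and 12. Terms: treatment, visit, treatment by visit, baseline score by visit, age group and symptom-duration group.
3. From the same model, report the weeks 4–12 average and the week-4 difference as supportive. The week-4 difference keeps the FAS ≤21 comparison linked to the full scale.
4. Use the same model for each SF-36 domain.
5. Keep the treatment-by-time test as supportive, stating whether it is Greenhouse-Geisser corrected or multivariate.

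The cost is new wording, Human Subjects Committee approval and a few degrees of freedom; subjects, visits and data are unchanged. Adding the strata gains little unless they are strongly prognostic: week-12 power at CS 0.6 rises from 0.79 to 0.81 if each shifts the 12-week change by 2 points, and from 0.69 to 0.80 at 5 points.

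The main downside is that the week-12 contrast has almost no power, about 5%, for an effect present only at week 4. That is why items 3 and 5 stay in the plan. The amendment should also say whether the model uses observed or carried-forward scores; which is preferable is a separate question.
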